4.4 Safety Endpoint

Adverse events, including serious adverse events, reoperations and revisions, up to 24 months.

5 Treatment Failure Definition

- For both Agili-C™ & SSOC groups: any secondary invasive treatment in the treated joint, regardless if related or unrelated to the original treatment, will be considered a treatment failure. Invasive interventions include: open procedure, mini-open procedure, arthroscopic procedure and intra articular injections, such as: HA, PRP, stem cells and steroids.
- Additionally, for the Agili-C™ arm: failure to implant the device in indicated patients will be considered a treatment failure. However, failure to implant the device in contraindicated patients/conditions will not be considered a treatment failure.

6 Randomization

Subjects will be randomized to either receive the Agili-C™ device or the control arm SSOC in a 2:1 ratio. Subjects will be randomized by site using variable block sizes of 3 and 6.

7 Interim Analyses

Details for the interim analyses, decision criteria, models, imputation procedures, simulations and operating characteristics for the design are included in the Adaptive Design Report attached as Appendix 1. The interim analyses will be conducted by an independent statistician and reviewed by the Endpoint Adjudication Committee (EAC).

The interim analyses, as described in Appendix 1, include only the primary endpoint - change from baseline to 24 months in average overall KOOS score. For the EAC review, we will also summarize and test the first confirmatory secondary endpoint - change from baseline to 24 months in KOOS Pain subscore, using a Bayesian posterior probability of superiority. For this secondary confirmatory endpoint, the interim analysis will NOT include a longitudinal model to multiply impute incomplete observations. However, similarly to the primary outcome, we will consider any treatment failures to have the change from baseline to 24 months Pain subscore replaced with their baseline value. At the earlier interim analyses, there may be only a few

subjects that have reached 24-months of follow-up. If fewer than 30 subjects have completed follow-up at an interim analysis, no testing of the first confirmatory secondary endpoint will be performed and only descriptive statistics will be provided to the EAC.

Additional descriptive summaries of safety outcomes and other secondary outcomes may be included in the interim analysis reports reviewed by the EAC as supplemental information. No testing will be performed on these other endpoints; only summaries will be presented.

8 Sample Size

Sample size justification is provided in the Adaptive Design Report attached as Appendix 1.

The sample size selection procedure was selected to obtain approximately 80% power for 2:1 randomization with an alternative hypothesis corresponding to an 8-point improvement in 24 month KOOS, and assuming a 15% treatment failure rate in each study arm (thus the 8 point difference is prior to baseline imputation for treatment failures). The standard deviation in each study arm was assumed to be 23.

Details of the operating characteristics of the model, including simulations justifying the type I error rate of 2.5%, can be found in the Adaptive Design Report in Appendix 1.

9 Statistical Analyses

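### Read literally, the interim KOOS Pain test in SAP section 7 counts treatment failures as they occur but non-failures only at 24 months, so failures are over-represented in the probability shown to the EAC

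*SAP*

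**What the plan says.** SAP section 7 states that the interim analyses in Appendix 1 "include only the primary endpoint - change from baseline to 24 months in average overall KOOS score". For the EAC it adds a second analysis: "we will also summarize and test the first confirmatory secondary endpoint - change from baseline to 24 months in KOOS Pain subscore", by a Bayesian posterior probability of superiority. Two rules then govern who contributes to that analysis.

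- Incomplete observations: "the interim analysis will NOT include a longitudinal model to multiply impute incomplete observations".
- Failures, introduced as an exception to the first rule: "we will consider any treatment failures to have the change from baseline to 24 months Pain subscore replaced with their baseline value".

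The test is suppressed, and only descriptive statistics are given, "If fewer than 30 subjects have completed follow-up at an interim analysis". Section 7 does not otherwise define the analysis set.

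Under SAP section 5, "any secondary invasive treatment in the treated joint, regardless if related or unrelated to the original treatment, will be considered a treatment failure". Such an event can happen at any time after surgery.

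**The concern.** The two rules make inclusion depend on the outcome. Take two subjects enrolled on the same day. One has a secondary invasive treatment at Month 3 and receives a value straight away. The other does well and contributes nothing until a 24-month score exists. The analysed set is then the 24-month completers plus every failure so far, which is neither the randomised cohort nor the cohort that has reached 24 months.

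At stake is whether the posterior probability given to the EAC describes the 24-month Pain difference at all. The distortion is largest at the earliest looks. The 30-subject threshold does not prevent it, because it counts completed follow-up and says nothing about the make-up of the analysed set.

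**Working it through.** **Inputs from the SAP (section 8).** An 8-point difference before failures are set to baseline, SD 23, 2:1 allocation, and "assuming a 15% treatment failure rate in each study arm". The minimum sample size is 250 (section 1.1). The effect and failure rate are planning values for overall KOOS; the SAP gives none for Pain, so they serve here as a stand-in.

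**Assumed (not in the documents).** 250 subjects, even accrual over 24 months, failures evenly spread over 24 months in both arms, no dropout.

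**The plan's own figure.** With failures scored as zero change, the planned difference is 8 x 0.85 = 6.8. A fixed 2:1 design with one-sided alpha 0.025 and 80% power needs 1.5 x (1.960 + 0.842)² x 23² / 6.8² = 135 controls, or 405 in total. Power is 59.6% at 250 and 87.6% at 500. The stated power of about 80% is therefore plausible for an adaptive 250 to 500 design. It cannot be reproduced exactly, because the simulations are in Appendix 1, which is not among the documents.

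**Failure share under the literal rule.** At study month T, follow-up is uniform from T - 24 to T. Let c be the proportion past 24 months and G the mean of min(follow-up/24, 1), which is the proportion of eventual failures that have already occurred. Then

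- share s = 0.15G / (0.15G + 0.85c)
- expected difference = 8 x (1 - s), since failures contribute zero change and s is the same in both arms.

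At month 27, c = 3/24 = 0.125 and G = 0.875 x (3 + 24)/(2 x 24) + 0.125 = 0.617.

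| Study month | Past 24 months | G | 0.15G | 0.85c | Share s | Difference |
|---|---|---|---|---|---|---|
| 27 | 31 | 0.617 | 0.093 | 0.106 | 47% | 4.3 |
| 28 | 42 | 0.653 | 0.098 | 0.142 | 41% | 4.7 |
| 30 | 63 | 0.719 | 0.108 | 0.213 | 34% | 5.3 |
| 36 | 125 | 0.875 | 0.131 | 0.425 | 24% | 6.1 |
| 48 | 250 | 1.000 | 0.150 | 0.850 | 15% | 6.8 |

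At month 27 the set holds about 250 x (0.093 + 0.106) = 50 subjects, of whom about 23 are failures.

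**Sensitivity to timing.** At month 27 the share is 35% (5.2 points) if all failures fall in months 12 to 24, and 55% (3.6 points) if all fall in months 0 to 12. With accrual over 36 months it is 35% (5.2 points) at month 30, 26% (5.9) at month 36 and 19.5% (6.4) at month 48.

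**Unequal failure rates.** Assume 36-month accrual, month 30, and non-failure changes of 28 (Agili-C) and 20 (SSOC). Among enrolled subjects, G = 0.8 x 0.5 + 0.2 = 0.6 and c = 0.2. A 21% failure rate gives s = 0.126/(0.126 + 0.158) = 0.444. A 7% rate gives s = 0.042/(0.042 + 0.186) = 0.184.

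- Agili-C 21%, SSOC 7%: true difference 28 x 0.79 - 20 x 0.93 = 3.5; shown 28 x 0.556 - 20 x 0.816 = -0.7.
- Agili-C 7%, SSOC 21%: true difference 28 x 0.93 - 20 x 0.79 = 10.2; shown 28 x 0.816 - 20 x 0.556 = 11.7.

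**Equal rates and equal non-failure means.** Both the true and the shown difference are zero, so there is no bias.

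**Same date rule for everyone.** s = 0.15c / (0.15c + 0.85c) = 15%, and the difference is 6.8 at every look.

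**The case against.** The strongest objection is that section 7 says what value a failure receives, not when it enters. The endpoint is a 24-month change, and the sentences that follow describe the available data as subjects who have reached 24 months. A set limited to those subjects is a possible reading, and under it the over-representation disappears. This stands as a limit: immediate entry is an inference from the wording. The literal reading remains the more natural one, because the failure sentence carries no time condition and is framed as an exception to the rule on incomplete data. SAP section 9.1.1 also treats failure imputation as what makes a subject evaluable for the full analysis set. Two programmers could fairly produce two different probabilities.

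The illustration also has limits. Its inputs are overall-KOOS planning values with assumed accrual and failure timing. If the threshold of 30 counts only non-failing completers, month 27 (250 x 0.106, about 27) falls just short and the month 28 row is the first that applies. Sampling noise at such looks is large: with 30 completers split 20:10, the standard error is 23 x sqrt(1/20 + 1/10) = 8.9 points, against a shift of about 2.5.

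A reader might infer that the interim decisions or the trial's conclusions are compromised. The documents do not support that. Section 7 ties no stopping rule to Pain, and the Appendix 1 analyses cover only the primary endpoint. At the final Pain analysis (SAP sections 9.4 and 10.3) all subjects have completed follow-up and dropouts are imputed.

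Finally, the looks are probably past: Protocol section 10.7.1 already uses Month 24 results from 160 and 79 subjects. That changes the remedy, not the point.

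**Conclusion.** The point holds as a defect in a stated rule for a supplementary display. On the literal reading, failures make up about 47% down to 24% of the analysed set instead of 15% as the number past 24 months grows from about 31 to 125. The expected difference is then 4.3 to 6.1 points instead of 6.8, under the stand-in values and assumptions listed.

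It would be wrong to infer that the shown difference is always biased, or always biased in one direction. With equal failure rates and equal non-failure means it is unbiased. With equal rates and a real effect it is pulled toward zero. With unequal rates it can be inflated, shrunk or reversed. The reach is confined to the probability shown to the EAC, so this is a low-severity correction.

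**What to change.** In SAP section 7, define the interim Pain set by date: subjects whose 24-month visit window (24 months after the procedure plus the allowed 16 weeks) has closed at the data cut-off, failures and non-failures alike. Including the 16 weeks matters, because a cut at exactly 24 months would still count failures while non-failures await a late visit. Score failures as zero change; the current sentence literally replaces a change score with a baseline value. Count the 30-subject threshold in the same set, and list failures among subjects not yet due separately.

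Alternatively, apply the primary endpoint's longitudinal imputation model to all randomised subjects. This also covers dropouts, who would have no value in the restricted set, but it relies on the model being right.

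The cost is a sentence or two in the SAP and one date filter. The downside of the date rule is fewer subjects in the early tests. At the assumed 250/24 = 10.4 subjects a month, waiting 16 weeks (about 3.7 months) holds back up to about 38 subjects at a look, so the first test may come later.

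If the interims have already been run, state which set was used and rerun the test on the restricted set.

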## 10.5 Primary Analysis

The primary analysis will be conducted on the full analysis set using the same statistical models that were used in the analyses in the pivotal trial. The primary goal of the post approval study is to demonstrate superiority of the Agili-C™ device relative to SSOC at Month 60 by testing the hypothesis:

$$H_0 : \theta_1 = \theta_0 \text{ vs. } H_A : \theta_1 > \theta_0.$$

Where  $\theta_1$  and  $\theta_0$  are the mean improvements in KOOS Overall score from baseline to Month 60 for Agili-C™ and SSOC subjects, respectively. To test this hypothesis, the posterior probability of superiority:  $Pr(\theta_1 > \theta_0 | \text{Data})$  will be evaluated. The post approval study will have met its primary objective if the posterior probability exceeds 0.975 at the final analysis.

As noted above, subjects with ‘treatment failure’ have subsequent outcome values set to their baseline value. The analysis plan specifies that subjects with otherwise missing values are to have their missing values imputed through the Bayesian model. Month 60 imputations are informed by observed data at earlier time points. Non-informative priors distributions are used in all analyses. The SAS procedure PROC BGLIMM (SAS Institute) will be used to determine the posterior probability that Agili-C™ is superior to SSOC in terms of mean changes from baseline to Month 60 in KOOS Overall Score. The BGLIMM procedure is a sampling-based procedure that provides Bayesian inference for generalized linear mixed models (GLMMs). GLMMs are hierarchical models that combine a generalized linear model with normally distributed random effects. The “Bayesian approach estimates the joint posterior distribution of all parameters in a model, including all fixed- and random-effects parameters. The Monte Carlo method numerically integrates out the random effects and propagates the uncertainties to the marginal posterior of the fixed-effects parameters. PROC BGLIMM uses efficient Markov chain Monte Carlo (MCMC) sampling tools to estimate the posterior marginal distributions and use them for further inference” (SAS® 9.4 Help and Documentation ).

CLN0021-US-Investigational Plan		Document Number: CLN-0000002
 CartiHeal		Document Version: 8.0 Effective Date: 08-Jun-2022 (GMT+2) Page 50 of 80
A Post Approval Multicenter Open-label Randomized Controlled Trial of Agili-C™ vs. Surgical Standard of Care (SSOC) for the Treatment of Joint Surface Lesions of the Knee		

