1.1 Overview

This is a multicenter, 2:1 randomized, open-label, controlled clinical trial of the Agili-C™ device for the treatment of joint surface lesions of the knee. Subjects will be randomized to either the investigational Agili-C™ device or the surgical standard of care (SSOC) control group, with twice as many subjects allocated to the investigational device. The trial has a flexible sample size that will be determined adaptively using a “Goldilocks” strategy. A minimum of 250 subjects, and up to a maximum number of 500 subjects, will be randomized.

This is an adaptive trial design, with interim analyses which allow for early stopping of the trial for futility, or for early stopping of enrollment, but continuing follow-up, for expected success. The primary outcome, change from baseline in overall KOOS score will be assessed at 24 months. Table 1 presents the schedule of study activities.

Table 1.

Procedures	Screening Visit	Final Screening/Procedure Visit	2 week Post-Procedure Visit (\pm 1.5 weeks)	3 ^μ , 6 ^Λ months post procedure (\pm 12 weeks, 12 and 18 Months Post-Procedure Visit (\pm 16 weeks)	24 Months Post-Procedure Visit (\pm 16 weeks)	Annual Post-24 months Visit [§] (12 months \pm 16 weeks)	Unscheduled Visit
Number of Visit	Visit 1	Visit 2	Visit 3	Visits 4-7	Visit 8	Visits 9+	
Obtain Informed Consent	X						
Assignment of Subject Number	X						
Review Inclusion/Exclusion criteria	X	X (intra operative)					
BMI	X [@]						
Medical History	X						
Baseline MRI	X*						
MRI according to CartiHeal protocol				X**	X**		X***
Defect Fill Evaluation according to MRI, off-site				X ^{**,∞}	X**		
Baseline standing X-ray (AP & Lateral)	X*						
Weight bearing AP & Lateral X-ray			X [#]	X [∞]	X		X***
IKDC Knee Examination form 2000 (Surgeon)	X			X [∞]	X		X
OA Classification Kellgren-Lawrence score, off-site	X						
ICRS Cartilage Injury Standard Evaluation Form 2000 (Subject)	X						
ICRS Knee History	X						

Registration (Surgeon)							
SF-12 v2	X			X [∞]	X	X	
Procedures	Screening Visit	Final Screening/Procedure Visit	2 week Post-Procedure Visit (\pm 1.5 weeks)	3 ^μ , 6 [^] months post procedure (\pm 12 weeks, 12 and 18 Months Post-Procedure Visit (\pm 16 weeks)	24 Months Post-Procedure Visit (\pm 16 weeks)	Annual Post-24 months Visit ^{\$} (12 months \pm 16 weeks)	Unscheduled Visit
2000 IKDC Subjective Knee Evaluation Form	X			X [∞]	X	X	
KOOS Subscales	X			X [∞]	X	X	
Tegner score	X			X [∞]	X	X	

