9.1 Analysis Populations

9.1.1 Full Analysis Set Population

The full analysis set (FAS) will consist of all treated subjects in the Agili-C™ arm and all treated subjects in the SSOC arm, for whom there is a valid overall KOOS score at baseline and at least one valid overall KOOS score post-baseline. A treated subject is defined as any subject who was randomized to any of the groups, and is not defined as a subject with major entry violation (as defined below).

In the FAS population, subjects who are treatment failures (as defined in Section 5.0) will have their 24-month KOOS score imputed as their baseline KOOS score. Thus, the treatment failure imputation will provide at least one valid overall KOOS score post-baseline and these subjects will be included in the primary analysis FAS population.

For all analyses performed on the FAS population, subjects will be analyzed according to the treatment arm to which they were randomized (regardless of the treatment actually received).

Consistent with ICH-E9, subjects with major entry violations will be excluded from FAS. Major entry violation is defined by having the potential to affect trial results and the decision of whether an entry violation is considered major will be performed by the Medical Director according to the following parameter - enrolment of subject with severe exclusion criteria, such as:

1. Bony defect depth deeper than 8mm
2. Uncontained lesion - lack of vital bone wall, at least 2mm thick, completely surrounding the lesion
3. Inability to position the implant 2mm recessed relative to the articular surface
4. Articular cartilage lesions in the tibia or the patella, ICRS grades IVa or above
5. Systemic cartilage and/or bone disorder

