9.4 Confirmatory Secondary Analyses

This trial has 4 confirmatory secondary endpoints that, for the final analysis, will be tested on the FAS population hierarchically in the order presented below to preserve overall Type I Error = 0.05.

The following three pairs of confirmatory hypotheses, relating to continuous endpoints, will be tested similarly to the primary endpoint final analysis as described in the preceding section:

Confirmatory I

H_0 : Change in KOOS Pain (Agili-CTM) at 24M \leq Change in KOOS Pain (SSOC) at 24M

H_1 : Change in KOOS Pain (Agili-CTM) at 24M $>$ Change in KOOS Pain (SSOC) at 24M

Confirmatory II

H_0 : Change in KOOS QOL (Agili-CTM) at 24M \leq Change in KOOS QOL (SSOC) at 24M

H_1 : Change in KOOS QOL (Agili-CTM) at 24M $>$ Change in KOOS QOL (SSOC) at 24M

Confirmatory III

H_0 : Change in KOOS ADL (Agili-CTM) at 24M \leq Change in KOOS ADL (SSOC) at 24M

H_1 : Change in KOOS ADL (Agili-CTM) at 24M $>$ Change in KOOS ADL (SSOC) at 24M

Confirmatory IV

H_0 : Response Rate (Agili-CTM) at 24M \leq Response Rate (SSOC) at 24M

H_1 : Response Rate (Agili-CTM) at 24M $>$ Response Rate (SSOC) at 24M

For Confirmatory Endpoints I-III, testing will be performed by calculating the posterior probabilities of superiority in a manner similar to the primary endpoint. (See Adaptive Design Report in the Appendix for Details). A confirmatory secondary endpoint will be considered a success if the posterior probability exceeds 0.975. Like the primary endpoint final analysis, treatment failures will have their outcome replaced with their baseline value. And for this final analysis, all subjects will have completed follow-up. However, subjects that drop out will be multiply imputed using the longitudinal model with weakly informative priors on all parameters (see Section 9).

For Confirmatory IV, the analysis will be similar, but adjusted for the dichotomous nature of the data. Let p_0 and p_1 be the responder rates at 24 months for SSOC and Agili-C, respectively. We test the hypothesis

$$H_0: p_1 = p_0 \quad \text{vs.} \quad H_A: p_1 > p_0$$

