We model the responder rate independently for each arm using non-informative priors, $p_j \sim \text{Beta}(0.5, 0.5)$ for arm j . Success corresponds to posterior probability $\text{Pr}(p_1 > p_0 | \text{Data}) > 0.975$. For this analysis, treatment failures will be imputed as non-responders. Subjects with missing data due to drop out will be handled using multiple imputation, as described in Section 9. The analyses for the Confirmatory Secondary Endpoints will be repeated on the PP population.

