10.2 Primary Analysis

At the primary (final) analysis, all subjects will have completed full follow-up time. Treatment failures will have their outcome replaced with their baseline value. If some subjects drop out and missing data is present after performing the steps mentioned above (if necessary), any remaining missing data will be handled through multiple imputation, however only weakly informative priors will be used for this final analysis, as follows:

$$\alpha_t \sim N(0, 1) \text{ for } t = 6, 12, 18 \text{ months}$$

$$\lambda_t^2 \sim IG(0.5, 312) \text{ for } t = 6, 12, 18 \text{ months}$$

$$\tau^2 \sim IG(0.5, 312)$$

See the adaptive design report in appendix 1 for full details of the model, as well as the informative prior distributions to be used at the interims.

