10.3 Confirmatory Secondary Analyses

Missing data for the confirmatory secondary endpoints at the final analysis will be handled in a manner similar to the primary analysis. Treatment failures will have their outcome replaced with their baseline value. If necessary, we will next perform the steps for missing information with the KOOS subscale and overall KOOS score as described above. If missing data is still present due to subject drop out, the missing data will be handled through multiple imputation, using only weakly informative priors as in described above.

For Secondary Confirmatory Endpoint IV, the analysis method will differ slightly due to the dichotomous nature of the data. Treatment failures and dropouts will be imputed as described above for the continuous change from baseline endpoint. After imputation, the outcomes will be dichotomized for the purpose of testing the responder rate hypothesis.

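### SAP 7 sets a treatment failure's KOOS Pain change, rather than the Month-24 score, to the baseline value: a drafting error that contradicts SAP 9.1.1 and, read literally, counts a failure as a 20 to 65 point gain in the interim Pain test

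*SAP*

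**What the plan says.** SAP 7 (Interim Analyses) adds a test of the first confirmatory secondary endpoint, KOOS Pain, for EAC review. It applies once at least 30 subjects have completed follow-up. For that test the rule is "any treatment failures to have the change from baseline to 24 months Pain subscore replaced with their baseline value". The same sentence says that this handling follows the primary outcome.

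Other places state the failure rule differently:

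- SAP 9.1.1: failures "will have their 24-month KOOS score imputed as their baseline KOOS score". The score is replaced, so the change is 0.
- Protocol 10.4: the questionnaire scores of failures are imputed as their baseline scores, which also gives change 0.
- SAP 9.4, for the continuous confirmatory endpoints: "treatment failures will have their outcome replaced with their baseline value". SAP 10.2 says the same for the primary analysis: "Treatment failures will have their outcome replaced with their baseline value". SAP 10.3 repeats it for the confirmatory secondaries.
- SAP 1.1 uses the word outcome for a change: "The primary outcome, change from baseline in overall KOOS score will be assessed at 24 months".
- Responder endpoint: SAP 9.4 says "treatment failures will be imputed as non-responders". SAP 10.3 says "Treatment failures and dropouts will be imputed as described above for the continuous change from baseline endpoint" and dichotomises afterwards.

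**The concern.** The object replaced in SAP 7 is the change, not the Month-24 score. On KOOS Pain higher is better and a positive change is a gain. Setting the change to the baseline value therefore credits a subject who needed a second invasive intervention with an improvement as large as their baseline score. The rule in SAP 9.1.1 credits none. The two cannot both be followed.

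If a programmer took SAP 7 at its word, both arms' mean Pain change would be inflated and the comparison shown to the EAC would move towards the arm with more failures. Equal failure rates cannot be taken for granted: under SAP 5, failure to implant in an indicated patient counts as a failure, and this can occur only in the Agili-C arm.

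The looser wording in SAP 9.4, 10.2 and 10.3 does not say that the change is replaced. It does leave the word outcome open, and SAP 1.1 attaches that word to a change.

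**Working it through.** **Plan's own figure.** SAP 7 gives none for this rule. The nearest is the power of about 80% in SAP 8 (8 points on overall KOOS, SD 23, 15% failures per arm, 2:1, N from 250 to 500). If failures contribute change 0, the effect dilutes to 0.85 × 8 = 6.8. For a fixed sample, power = Φ(6.8 / [23 × √(1/n₁ + 1/n₂)] − 1.96), which gives 59.6% at N = 250 and 87.6% at N = 500. The stated 80% lies between these. It cannot be reproduced exactly, because it rests on the Adaptive Design Report, which is not in the text available. Nor does it show which reading was used: with 15% failures in each arm and a common mean baseline B, the literal reading gives (0.85·m_A + 0.15·B) − (0.85·m_S + 0.15·B) = 0.85 × 8 = 6.8 as well, where m_A and m_S are the mean changes of non-failures.

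**Inputs for the Pain rule.**

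- Baseline Pain B from 20 to 65, on a scale from 0 to 100 with higher better (Protocol 5.14, exclusion 1).
- Failure rate f = 15% per arm (SAP 8).

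**Step 1: one subject.** Score set to baseline: change = B − B = 0. Change set to baseline: change = B, so the implied Month-24 score is B + B = 2B.

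| Baseline B | Change, SAP 9.1.1 rule | Change, SAP 7 literal | Implied Month-24 score, literal |
|---|---|---|---|
| 20 | 0 | +20 | 40 |
| 42.5 (midpoint) | 0 | +42.5 | 85 |
| 65 | 0 | +65 | 130 |

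The implied score exceeds 100 whenever B is above 50.

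**Step 2: one arm's mean.** Inflation = f × B: 0.15 × 20 = 3.0; 0.15 × 42.5 = 6.4; 0.15 × 65 = 9.75 points.

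**Step 3: difference between arms (Agili-C minus SSOC).** Shift = f_A·B_A − f_S·B_S, where B_A and B_S are the mean baselines of the failures. With a common mean baseline this is (f_A − f_S) × B.

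- 15% in both arms (SAP 8): shift 0.
- Assumed 10% Agili-C, 20% SSOC: −0.10 × 20 = −2.0 to −0.10 × 65 = −6.5.
- Assumed 20% Agili-C, 10% SSOC: +2.0 to +6.5.

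**Step 4: responder endpoint.** With the score set to baseline, the change is 0. That is below the 30-point threshold, so the subject is a non-responder, and SAP 10.3 agrees with SAP 9.4. With the change set to baseline, a failure with overall KOOS of 30 or more at baseline would be a responder, against SAP 9.4. The conflict exists only under the literal reading.

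**The case against.** The strongest reply is that the intent is plain and the slip is harmless. The SAP 7 sentence ties itself to the primary outcome, for which SAP 9.1.1 is explicit. SAP 9.4 and 10.3 are tied to the primary analysis in the same way, and SAP 9.10 also imputes failures with their baseline score. The literal rule can produce scores off the scale, so a competent programmer would notice. The affected test is supplementary: the formal interim analyses use the primary endpoint only. Protocol 10.7.1 already reports Month-24 results, so the interim stage is past. SAP 7 also places the interim imputation details in the Adaptive Design Report, which cannot be checked here.

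Most of this stands, and it limits the point to a drafting error. It does not remove the point, because the sentence is an operative rule and says something different from SAP 9.1.1.

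A reader might go further in three ways that the documents do not support.

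- *That failures were scored as gains, or that the final primary analysis rewards failure.* There is no evidence of either, and SAP 9.1.1 settles the primary rule.
- *That the error carries into the Month-60 analysis, because Protocol 10.5 says failures "have subsequent outcome values set to their baseline value".* That sentence refers back to the rule in Protocol 10.4, and Protocol 10.5 later says that scores after failure are imputed to baseline. It needs no correction on this point.
- *That 3.0 to 9.75 points is comparable with the 8-point design effect.* The first is inflation of one arm's mean on KOOS Pain; the second is a between-arm difference on overall KOOS. The documents give no eligibility range for overall KOOS.

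**Conclusion.** The point holds as an internal contradiction confined, in explicit form, to the interim KOOS Pain test in SAP 7. The literal wording and the SAP's own rule differ by 20 to 65 points for each failure who met the Pain eligibility limits; a subject enrolled in violation could fall outside that range. The effect on one arm's mean scales with the 15% planning failure rate. Any between-arm shift depends on unequal failure rates or unequal baselines among failures, and the documents supply neither; the 10% and 20% rates used above are assumptions. The interim decisions on the primary endpoint and the Month-60 analysis are not affected. SAP 9.4, 10.2 and 10.3 are ambiguous rather than wrong, and the responder rules agree once the score reading is fixed.

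**What to change.** - SAP 7: replace the clause with *the Month-24 Pain subscore is set equal to the baseline Pain subscore, so the change from baseline is 0*.
- SAP 9.4, 10.2 and 10.3: replace the word outcome in the failure rule with *post-failure score (change = 0; non-responder)*, so that the continuous and responder rules read the same way.
- Protocol 10.5: no change on this point.

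The cost is a few words in four SAP sections. No new data are needed, and the analysis stays as SAP 9.1.1 and Protocol 10.4 already define it. When making the edit, check that the Adaptive Design Report uses the same wording.
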